7.4.1 Baseline

The baseline value will be the last non-missing value collected before study treatment. This may be collected at the Baseline visit, Pre-Procedure visit, or an unscheduled visit.

Change from baseline will be calculated as observed value – baseline value. Percent change from baseline will be calculated as change from baseline divided by the baseline value, multiplied by 100.

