9.2 Multiplicity Adjustment

The fixed-sequence procedure[1,2] will be used to evaluate the following secondary endpoints. Each of these tests will be tested at the same significance level ($\alpha=0.05$) in this predetermined order. Each endpoint is only tested if the prior endpoint is successful ($p \leq 0.05$). This procedure does not inflate the Type I error rate since the sequence is prospectively specified and no further testing is performed once an endpoint in the sequence fails to show significance ($p > 0.05$)[2]. All tests will be performed on the ITT population. If sufficient data have not been collected during this study to permit the evaluation of a given endpoint, that endpoint should be skipped and the subsequent endpoint evaluated:

- 1) Achievement of $\geq 90\%$ reduction in baseline AF burden at 12 months post-procedure, where subjects with new or increased dosage of Class I/III AADs during the efficacy evaluation period are categorized as not achieving $\geq 90\%$ reduction, using the Fisher's Exact test as described in Section 9.4.1.

- 2) AF freedom during efficacy evaluation period, using the chi-square or Fisher's Exact test as described in Sections 9.4.5 and 9.1, where subjects with new or increased dosage of Class I/III AADs during the efficacy evaluation period are categorized as not achieving AF freedom.
- 3) Achievement of $\geq 90\%$ reduction in baseline AF burden at 12 months post-procedure, regardless of Class I/III AAD usage, using the Fisher's Exact test as described in Section 9.4.1.
- 4) AF freedom during efficacy evaluation period, using the chi-square or Fisher's Exact test as described in Sections 9.4.5 and 9.1, regardless of Class I/III AAD usage.
- 5) Change in AFSS composite score at 12 months post-procedure, using an ANCOVA model as described in Section 9.4.3.
- 6) Change in SF-36 physical health composite score at 12 months post-procedure, using an ANCOVA model as described in Section 9.4.2.
- 7) Change in SF-36 mental health composite score at 12 months post-procedure, using an ANCOVA model as described in Section 9.4.2.
- 8) Change in distance walked during six-minute walk test at 12 months post-procedure, using an ANCOVA model as described in Section 9.4.4.
- 9) Change in left ventricular ejection fraction (LVEF) at 6 months post-procedure, as described in Section 9.5.2.
- 10) Atrial remodeling assessed by a decrease in left atrial size at 6 months post-procedure, as described in Section 9.5.3.

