- 11) Freedom from AF/AFL/AT requiring intervention (emergency visits, cardioversion, urgent care visit, re-ablation, etc.), data permitting.
- 12) Achievement of $\geq 75\%$ reduction in baseline AF burden at 12 months post-procedure, where subjects with new or increased dosage of Class I/III AADs during the efficacy evaluation period are categorized as not achieving $\geq 75\%$ reduction, using the Fisher's Exact test as described in Section 9.4.1.
- 13) Achievement of no more than 12% AF burden at 12 months post-procedure, where subjects with new or increased dosage of Class I/III AADs during the efficacy evaluation period are categorized as not achieving $\leq 12\%$ AF burden, using the Fisher's Exact test as described in Section 9.4.1.
- 14) Freedom from stroke-relevant AF/ AFL/AT-duration (cutoff of 1 hour), data permitting.
- 15) Regression of AF: conversion of persistent to paroxysmal AF, data permitting.
- 16) Prevention in AF progression: time to first episode of persistent AF, data permitting.

Multiplicity tests #1-16 are based on the 12 month data analyses, and will be performed at that time. The following multiplicity tests are based on data collected at the 18 month visit. Therefore, they will be performed after data collection and cleaning is completed for the 18 month visit. As described above, these endpoints will only be evaluated using the fixed-sequence procedure if all of the prior endpoints are significant.

- 17) Success or failure to achieve a 90% reduction from baseline AF burden with and without Class I/III AADs at 18 months post-procedure, where subjects with new or increased dosage of Class I/III AADs during the efficacy evaluation period are categorized as not achieving $\geq 90\%$ reduction, as described in Section 9.5.1.
- 18) Change in number of hospitalizations for the 12 months post-procedure period (6 months to 18 months post- procedure) compared to the number of hospitalizations in the 12 months prior to the procedure, as described in Section 9.5.4, date permitting.
- 19) Change in rhythm disturbance treatments (e.g. electrical or pharmacological cardioversion, AAD therapy, supraventricular ablative therapy) 12 months post-procedure period (6 to 18 months post-procedure) compared to 12 months prior to the procedure, as described in Section 9.5.5, data permitting.

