9.4 Secondary Efficacy Analysis

All secondary analyses will be performed on the ITT population. These analyses may be repeated on the mITT and PP populations.

9.4.1 $\geq 90\%$ Reduction in AF Burden

The AF burden, as a percentage, is recorded on the Holter Monitor eCRF. The recorded values and percent change from baseline in AF burden will be summarized by time point at 6, 12, and 18 months post-procedure.

The percent change from baseline at 12 months will be categorized as $\geq 90\%$ reduction (percent change $\leq -90\%$) or $< 90\%$ reduction (percent change $> -90\%$). The proportion of subjects achieving $\geq 90\%$ reduction at 12 months will be compared between treatment arms using Fisher's Exact test.

This analysis will be repeated for the following subsets of subjects:

- Subjects who have taken a Class I/III AAD during the efficacy evaluation period (excluding previously failed Class I/III AADs with no increase in dosage).

- Subjects who have *not* taken a Class I/III AAD during the efficacy evaluation period (excluding previously failed Class I/III AADs with no increase in dosage).
- Subjects who have taken any Class I/III AAD during the efficacy evaluation period.

No imputation will be performed for missing data.

These analysis (on all subjects and the three subsets) will also be repeated where subjects with a new or increased dosage of Class I/III AADs during the efficacy evaluation period will be categorized as not having achieved $\geq 90\%$ reduction. This will be performed on the ITT population. No imputation will be performed for missing data.

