The change in the number of rhythm disturbance treatments between the two periods will be calculated for each subject as the number of rhythm disturbance treatments in the 6-18 month period minus the number of rhythm disturbance treatments in the 12 months prior to the study procedure. The change will not be calculated for subjects who withdraw from the study within 18 months after study procedure, and they will be excluded from analyses. No imputation will be performed.

The difference between treatment arms in the change in the number of rhythm disturbance treatments will be analyzed using a Poisson model with treatment arm and the number of rhythm disturbance treatments in the 12 months prior to the study procedure as covariates. This analysis will be performed on the ITT population.

9.5.6 **≥75% Reduction in AF Burden**

The percent change from baseline at 12 months will also be categorized as ≥75% reduction (percent change ≤ -75%) or <75% reduction (percent change >-90%). The proportion of subjects achieving ≥75% reduction at 12 months will be compared between treatment arms using Fisher's Exact test, as described in Section 9.4.1.

This analysis will be repeated for the subsets of subjects described for the analysis of 90% reduction of AF burden. No imputation will be performed for missing data.

9.5.7 **≤12% Overall AF Burden**

Subjects will be categorized as having no more than 12% AF burden or >12% AF burden at 6, 12, and 18 months. The proportion of subjects with >12% AF burden will be compared between treatment arms using Fisher's Exact test, as described in Section 9.4.1.

This analysis will be repeated for the subsets of subjects described for the analysis of

90% reduction of AF burden. No imputation will be performed for missing data.

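### SAP 9.5.6 gives the failure category of the 75% AF burden endpoint a cut-off of -90% instead of -75%, so reductions from 75% to just under 90% count as both success and failure

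*SAP*

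**What the plan says.** SAP 7.4.1 sets the sign convention: "Percent change from baseline will be calculated as change from baseline divided by the baseline value, multiplied by 100". Change is observed minus baseline, so a reduction in AF burden is a negative number.

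SAP 9.5.6 then defines two categories for the 12-month percent change:

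- success: "≥75% reduction (percent change ≤ -75%)"
- failure: "<75% reduction (percent change >-90%)"

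It continues: "The proportion of subjects achieving ≥75% reduction at 12 months will be compared between treatment arms using Fisher's Exact test". The same categories are to be reused for the subsets defined by Class I/III AAD use.

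The endpoint is also test 12 of the fixed sequence in SAP 9.2. There, subjects with a new or increased Class I/III AAD "are categorized as not achieving $\geq 75\%$ reduction, using the Fisher's Exact test as described in Section 9.4.1". On the error rate, SAP 9.2 says "Each of these tests will be tested at the same significance level ($\alpha=0.05$) in this predetermined order", and each test is carried out only if the one before it succeeded. Section 9.4.1, to which test 12 refers, gives cut-offs for the 90% endpoint only.

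**The concern.** Two categories of a binary endpoint must be disjoint and must together cover every value. Here the success category ends at -75% while the failure category begins just above -90%, so they overlap. The failure category also contradicts its own label, because an 80% reduction is not a reduction of less than 75%.

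How an overlapping subject is classified depends on the programming. Code that tests the success condition first counts the subject as a success. Code that tests the failure condition first counts the subject as a failure. Code that sets two separate flags counts the subject twice, and the category totals exceed the number of subjects.

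At stake is the meaning of test 12. If the failure line governs, only changes of -90% or lower remain as successes, and the 75% endpoint becomes the 90% endpoint under another name.

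**Working it through.** **Inputs.** The percent change formula is from SAP 7.4.1, the two 75% categories from SAP 9.5.6, the two 90% categories from SAP 9.4.1, and the content of tests 1 and 12 from SAP 9.2. Let x be the percent change from baseline at 12 months.

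**Step 1: control case.** SAP 9.4.1 defines success as x ≤ -90 and failure as x > -90. Each is the exact complement of the other, so overlap and gap are both empty. The form of definition is sound when the two numbers match.

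**Step 2: the 75% endpoint as printed.** Success is x ≤ -75 and failure is x > -90.

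- Overlap: {x ≤ -75} and {x > -90} together give -90 < x ≤ -75.
- Gap: no x has both x > -75 and x ≤ -90, so no value is left unclassified.

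A check over x from -100 to +50 in steps of 0.01 found the overlap running from -89.99 to -75.00, with no unclassified value.

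| x (%) | Success as printed (≤ -75) | Failure as printed (> -90) | Failure corrected (> -75) |
|---|---|---|---|
| -95 | yes | no | no |
| -90 | yes | no | no |
| -89.99 | yes | yes | no |
| -80 | yes | yes | no |
| -75 | yes | yes | no |
| -74.99 | no | yes | yes |
| -50 | no | yes | yes |

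As an invented example, a burden falling from 100% to 20% gives x = (20 - 100) / 100 × 100 = -80, which meets both printed definitions. A change of exactly -90% is a success only, so the affected band is a reduction of at least 75% and below 90%.

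**Step 3: the corrected pair.** With x ≤ -75 against x > -75, overlap and gap are both empty. The same grid found none of either.

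**Step 4: consequence for the sequence if the failure line governs.** Success becomes everything that is not x > -90, which is x ≤ -90. The two tests then compare as follows.

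| Feature | Test 1 | Test 12 under the failure line |
|---|---|---|
| Cut-off at 12 months | x ≤ -90 | x ≤ -90 |
| New or increased Class I/III AAD | not achieving | not achieving |
| Test | Fisher's exact | Fisher's exact |
| Population | ITT | ITT |
| Missing data | not imputed | not imputed |

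The two are the same test on the same data and give the same p-value. Test 1 must already have reached p ≤ 0.05 for the sequence to arrive at test 12, unless it was skipped for insufficient data, so the miscoded test 12 would pass automatically. The miscoding could not stop the sequence. It could let tests 13 to 19 proceed where a correctly coded 75% comparison might have failed.

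**Step 5: size.** Let b_T and b_C be the shares of evaluable treatment and control subjects who lie in the band and, for test 12, have no new or increased Class I/III AAD. Recoding them as failures lowers the success rates by b_T and b_C, and changes the difference between arms by -(b_T - b_C). The documents give neither share. Assumed values:

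| b_T | b_C | Change in treatment rate | Change in control rate | Change in difference |
|---|---|---|---|---|
| 0% | 0% | 0 | 0 | 0 |
| 5% | 5% | -5 points | -5 points | 0 |
| 10% | 5% | -10 points | -5 points | -5 points |
| 5% | 10% | -5 points | -10 points | +5 points |

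**The case against.** The strongest reply is that nobody would be misled. The section heading, both category labels, the success cut-off and the proportion to be compared all say 75%, and test 12 in SAP 9.2 describes its other category simply as not achieving a 75% reduction. Only one parenthesis disagrees. A program built on the success flag alone would give the intended result.

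The reach is also limited. This is an added exploratory endpoint, twelfth of nineteen in the sequence. Test 12 already counts subjects with a new or increased Class I/III AAD as failures, so within that test the ambiguity touches only band subjects without such use. In the 9.5.6 analysis without the AAD rule, it touches every band subject with data. Nor could a miscoded test 12 block the later tests, as step 4 shows.

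All of this stands, and it fixes the importance as low. It does not make the printed number right. Test 12 points to 9.4.1, which has no 75% cut-offs, so the defective sentence in 9.5.6 is the only place where a programmer finds them, and nothing elsewhere in the documents corrects it.

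**Conclusion.** The definition is wrong as written. The failure category of the 75% endpoint should begin above -75%, not above -90%, and as printed every reduction of at least 75% and below 90% falls in both categories. The overlap follows from the text alone and needs no assumption. That the figure came from SAP 9.4.1 is an inference from its correct use there.

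The numerical effect cannot be derived from the documents, because the number of subjects in the band is not given. Each 5% of an arm in the band (assumed) is worth 5 points on that arm's success rate, and the difference between arms moves only if the band shares differ. On the worst reading, test 12 repeats test 1 and passes without adding evidence. The primary endpoint, tests 1 to 11, the safety analysis and the sample size are untouched. This is a minor correction, but it belongs to an operative endpoint definition inside the alpha-controlled sequence.

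**What to change.** In SAP 9.5.6, change the failure cut-off from percent change above -90% to percent change above -75%. In SAP 9.2, test 12, add Section 9.5.6 to the cross-reference so that the reader is led to the 75% cut-offs as well as to the method in 9.4.1.

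The cost is one number and one section reference, with no effect on data collection or sample size. The change should be made before unblinding, so that no one can ask later whether the cut-off was chosen after the results were seen. If programs already exist, confirm that the 75% flag is derived from the -75% condition alone.

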9.5.8 Freedom from AF/AFL/AT Requiring Intervention

Freedom from AF/AFL/AT requiring intervention (emergency visits, cardioversion, urgent care visit, re-ablation, etc.) will be analyzed as described for the primary efficacy analysis, data permitting. Further details of the analysis will be finalized pending availability and usability of appropriate data.

9.5.9 Freedom from Stroke-Relevant AF/AFL/AT Duration

Freedom from stroke-relevant AF/AFL/AT duration (cutoff of 1 hour) will be analyzed as described for the primary efficacy analysis, data permitting. Further details of the analysis will be finalized pending availability and usability of appropriate data.

9.5.10 Conversion of Persistent to Paroxysmal AF

Conversion of persistent to paroxysmal AF will be analyzed for the ITT population, data permitting. Further details of the analysis will be finalized pending availability and usability of appropriate data.

9.5.11 Time to First Episode of Persistent AF

Time to first episode of persistent AF will be analyzed for the ITT population, data permitting. Further details of the analysis will be finalized pending availability and usability of appropriate data.

10 SAFETY ANALYSES

The Safety Population will be used for all summaries of safety assessments. No formal testing of statistical hypotheses will be performed on safety endpoints.

10.1 Major Adverse Events (MAEs)

MAEs (listed below and defined in Section 1.5.3 of the study protocol) will be adjudicated by the CEC. These adjudicated events will be recorded in a spreadsheet following the committee meeting and provided to the sponsor or designee after each meeting. The complete list of adjudicated events will be finalized prior to database lock and incorporated into an analysis dataset, separate from the adverse event dataset. MAEs will be summarized by event type and treatment arm, based on onset date:

- Date of study procedure through the 30th day post-procedure
- 31st day post-procedure through 12 months (365th day) post-procedure
- Overall

The MAEs for this study are as follows:

- Cardiac tamponade/perforation

- Severe pulmonary vein stenosis
- Excessive bleeding
- Myocardial infarction
- Stroke
- Transient ischemic attack
- Atrioesophageal fistula
- Phrenic nerve injury
- Death

The primary safety analysis will be to document an acceptable risk profile. This criterion will be defined as an acceptable level of MAEs. It is estimated that the true incidence rate for MAEs in this study population is no more than 12%. A 95% one-sided confidence interval for the investigational treatment arm based on a 102 subject sample size is 5%, resulting in an upper bound of MAEs being less than 20%. This result would document an acceptable risk profile for the investigational arm.

10.2 Adverse Events (AEs)

All reported terms (investigator descriptions) for AEs will be coded using the Medical Dictionary for Regulatory Activities (MedDRA) version 18.0. Treatment-emergent AEs (TEAEs) will be defined as AEs starting on or after the day of the study procedure. Relationship to EPi-Sense_AF device, relationship to endocardial catheter system, and relationship to study treatment/procedure, all reported as not related, unlikely related, possibly related, probably related, or definitely related, will be categorized as related (probably, possibly, or definitely), or unrelated (unlikely or not related).

All summaries of TEAEs will be presented by event type or system organ class (SOC) (as collected on the eCRF) and, for those in 'Other' event type, by SOC, preferred term (PT), and by treatment arm. Subjects will be counted at most 1 time per event type, SOC, or PT. Events will be summarized at the maximum severity or highest reported relationship, where applicable. The following summaries will be presented:

- TEAEs
- TEAEs with onset through the 30th day after study procedure
- Treatment-emergent serious adverse events (SAEs)
- Severe TEAEs
- TEAEs leading to discontinuation from the study
- TEAEs related to study treatment/procedure
- TEAEs related to endocardial catheter system
- TEAEs related to study device
- TEAEs by severity

All AEs will be listed by subject, event type, SOC, PT, verbatim term, and onset

date. Additional listings will be provided for SAEs, AEs leading to discontinuation, AEs leading to death, and unanticipated adverse device effects (UADE).

11 **INTERIM ANALYSES**

There are no planned interim analyses. Ad hoc analyses may be performed from time to time as necessary for regulatory agencies, safety review, corporate planning, etc. No adjustments to p-values in the final analyses will be made for such ad hoc analyses.

12 **PLANNED STUDY ANALYSES**

An analysis of the primary efficacy and safety endpoints, and additional other analyses performed on the data collected through the 12 month visit, will be performed after all subjects have completed their 12 month visit or discontinued. The data collected through the 12 month visit will be cleaned, quality checked, and frozen or locked prior to this analysis. All tables, listings, and figures will be produced at this time, even though some listings will only include limited data, such as the Long-Term Follow Up listing and analysis of hospitalization data, which compares occurrences in the 12 months prior to study procedure to those 6-18 months post-procedure.

A subset of the tables, listings, and figures may be produced after all subjects have completed their 18 month visit or discontinued. The data collected at the 18 month visit, and any unscheduled visits between the 12 and 18 month visits, will be cleaned and quality checked and frozen prior to this analysis. This subset is expected to include outputs related to concomitant medications, adverse events, hospitalizations, ECGs, and AF burden.

In addition, a subset of the tables, listings, and figures may be produced at intervals (for example, yearly) during the long-term follow-up period. This subset is expected to include the outputs related to long-term follow up.

The final analysis will be conducted after the last subject completes the 5 year follow-up visit or discontinues the study. This analysis will focus on the results from the long-term follow up data, but will also incorporate data collected earlier in the study. The remaining data will be cleaned and quality checked, and the entire database locked, prior to this analysis.

13 **DEPARTURES FROM PROTOCOL-SPECIFIED ANALYSES**

Protocol section 5.1 states that subjects who met intra-op exclusion criteria will be followed for 30 days post procedure (post-TEE or post-ICE) and will be included in the study safety analysis only. The Safety Population is defined as subjects who receive study procedure (EPi-Sense-AF or catheter ablation). Because subjects who meet intra-op exclusion criteria do not undergo a study procedure, they are not included in the

Safety Population and therefore, are not included in safety summary analyses. Instead, they will be included in data listings.

The mITT population has been clarified from the original text of including all study subjects who receive a randomized procedure and have at least one post-treatment follow-up visit, to state that it all randomized subjects who have at least one post-procedure follow-up visit after the 3 month blanking period, with non-missing efficacy results. The PP population definition has been clarified to state that having at least four of the five first year visits means at least four of the: 7 day, 1 month, 3 month, 6 month, and 12 month visits.

Protocol section 9.4 states that subjects who were randomized but have no post-blanking period assessments will be conservatively imputed as therapeutic failures at six months. Treatment success or failure is evaluated for the 3 to 12-month time period overall and not evaluated at the 6-month period specifically. Therefore, subjects who were randomized but have no post-blanking period assessments are imputed as therapeutic failures as described in Section 7.2, but are not specifically imputed as failure at 6 months.

Direct current (DC) cardioversion is listed as criteria for treatment failure in the protocol. The SAP expands that definition to include both electrical and pharmacologic cardioversion.

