#### **5.1 Procedure Intra-Op Exclusions**

Prior to initiating the study convergent procedure or the standalone endocardial catheter ablation procedure, review subject anatomy and TEE or ICE results to confirm that the subject does not meet any of the study intra-op exclusions listed below:

- Presence of left atrial thrombi per immediate pre-op Trans-Esophageal Echocardiograph (TEE) for the convergent procedure, and per TEE or Intra cardiac Echo (ICE) for the standalone endocardial catheter ablation procedure.
- Presence of adhesions that would prevent epicardial access to the pericardial space or the creation of the study recommended complete lesion pattern. (Convergent procedure arm only)

If the subject meets any of the above intra-op exclusions, the study procedures will not be performed. Subjects meeting the intra-op exclusions will be followed for 30 days post procedure and will be included in the study safety analysis only. Alternative treatment procedures for the subject's AF should be scheduled after the subject's 30 day follow-up for safety and study participation is completed.

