#### **Sub-Xyphoid Endoscopic Access**

Using standard surgical techniques for creating a pericardial window superior to the diaphragm, obtain access to the posterior surface of the heart. Create an incision immediately inferior to the xiphoid process. Direct visualization of the pericardium superior to the diaphragm can be achieved through the incision. The xiphoid process may be removed, dependent on patient anatomy. A 2 cm incision should be made in the pericardium to allow access for the cannula. The cannula provides direct access to the posterior surface of the heart and is sized to create space between the epicardium and the pericardium to visualize cardiac structures and manipulate the coagulation device alongside an endoscope, so all device manipulations are performed under direct visualization.

After obtaining Sub-Xyphoid access, the Epi-Sense®-AF Guided Coagulation Device with VisiTrax®, cannula, scopes and surgical instruments are used to create the epicardial lesion pattern.

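### SAP 13 removes every intra-op-excluded subject from the safety summaries, so an MAE in a convergent subject whose access was started and then aborted for adhesions would not count in the primary safety rate

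*SAP*

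**What the plan says.** Protocol 5.1 lists two intra-op exclusions. One is left atrial thrombus, assessed by TEE in the convergent arm and by TEE or ICE in the control arm. The other applies to the convergent arm only: "Presence of adhesions that would prevent epicardial access to the pericardial space or the creation of the study recommended complete lesion pattern". On timing it says: "Prior to initiating the study convergent procedure or the standalone endocardial catheter ablation procedure, review subject anatomy and TEE or ICE results". On analysis it says: "Subjects meeting the intra-op exclusions will be followed for 30 days post procedure and will be included in the study safety analysis only".

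SAP 13 declares a departure from that last rule. Its ground is: "Because subjects who meet intra-op exclusion criteria do not undergo a study procedure". Such subjects are therefore outside the Safety Population; they "are not included in safety summary analyses. Instead, they will be included in data listings". The rule makes no distinction by exclusion criterion or by how far access had gone.

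The Safety Population in Protocol 9.3.4 and SAP 5.4 is limited to subjects who received a randomized procedure. Neither section says whether a procedure that was begun and abandoned counts as received. SAP 3.2 runs the 30-day follow-up of excluded subjects from the TEE or ICE, and both Protocol 4.6 and SAP 3.2 have them replaced. The primary safety endpoint is the MAE incidence in the convergent arm from procedure to 30 days (Protocol 1.5.3, SAP 2.3.3). It is judged by a one-sided 95% upper bound below 20%, with 12% expected and 102 subjects (Protocol 9.7, SAP 10.1).

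**The concern.** The SAP's premise is that no excluded subject was exposed to a study procedure. If adhesions are found once access is under way, that premise fails. The subject has had an abdominal or sub-xiphoid incision, and possibly a pericardial one: for sub-xiphoid access Attachment A states, "A 2 cm incision should be made in the pericardium to allow access for the cannula".

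Harm from a failed access attempt is a risk of the convergent strategy. The MAE list includes excessive bleeding from a procedure-related injury, perforation, death, and phrenic nerve injury, which Protocol 1.5.3 defines to cover injury caused while reaching the heart. Under SAP 13 such an event would appear in a listing but not in the primary rate. Replacement would then fill the analysed arm with subjects in whom access succeeded.

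**Working it through.** **Could the adhesion exclusion be met after the incision?**

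- For: the thrombus criterion names its test (TEE or ICE); the adhesion criterion names none.
- For: Protocol 5.2 requires the exclusions to have been evaluated before the lesion pattern is created. It does not say before the incision.
- For: Protocol 5.2 starts total convergent procedure time at the abdominal incision, so an incised subject is already inside the procedure by the protocol's own clock.
- For: Protocol Table 1 ticks inclusion/exclusion criteria at the Procedure column as well as at Pre-procedure.
- Against: Protocol 5.1 puts the review before initiation. SAP 3.2 has the procedure scheduled and performed only after eligibility is settled.

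Discovery after incision is therefore a supported inference, not a stated fact.

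**Which passages would keep such a subject out of the rate?** SAP 13 does so directly. Protocol 9.3.4 and SAP 5.4 do so if an aborted procedure is not a received one. Protocol 8.0 starts primary safety collection at the start of the coagulation procedure, which read literally is later than the incision. SAP 3.2 starts the 30 days at TEE or ICE, which suits a thrombus finding but not an adhesion finding.

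**The plan's own safety figure.** Inputs from SAP 10.1: p = 0.12, n = 102, one-sided 95% (z = 1.645).

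Wald half-width = 1.645 × √(0.12 × 0.88 / 102) = 5.3%, so the upper bound is 17.3%. The stated 5% and the bound below 20% reproduce.

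**Effect of adding excluded subjects.** The documents give neither the number of started-then-aborted subjects (k) nor the MAEs among them (e), so both are assumed. With x MAEs in n subjects:

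- Wald bound = x/n + 1.645 × √[(x/n)(1 − x/n)/n]
- Exact (Clopper-Pearson) bound = 95th percentile of Beta(x + 1, n − x)

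| Start | k | e | Total | Rate | Wald bound | Exact bound |
|---|---|---|---|---|---|---|
| 12/102 | 0 | 0 | 12/102 | 11.8% | 17.0% | 18.4% |
| 12/102 | 1 | 0 | 12/103 | 11.7% | 16.9% | 18.2% |
| 12/102 | 1 | 1 | 13/103 | 12.6% | 18.0% | 19.3% |
| 12/102 | 2 | 2 | 14/104 | 13.5% | 19.0% | 20.2% |
| 12/102 | 3 | 2 | 14/105 | 13.3% | 18.8% | 20.1% |
| 12/102 | 3 | 3 | 15/105 | 14.3% | 19.9% | 21.1% |
| 12/102 | 5 | 0 | 12/107 | 11.2% | 16.2% | 17.5% |
| 12/102 | 5 | 2 | 14/107 | 13.1% | 18.4% | 19.7% |
| 13/102 | 0 | 0 | 13/102 | 12.7% | 18.2% | 19.5% |
| 13/102 | 1 | 1 | 14/103 | 13.6% | 19.1% | 20.4% |

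Worked line, 14/103 by Wald: 0.1359 + 1.645 × √(0.1359 × 0.8641 / 103) = 0.1359 + 0.0555 = 19.1%.

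At n = 102 a bound below 20% allows at most 13 MAEs by the exact method and 14 by Wald. Neither document names the method.

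**The case against.** The strongest reply is that the plan never intends an excluded subject to be cut. Protocol 5.1 places the review before initiation and says the study procedures will then not be performed, and SAP 3.2 sets the same order. On that sequence the SAP's premise is coherent. The SAP also did not invent the restriction: Protocol 9.3.4 already required receipt of a procedure, so the protocol was at odds with its own section 5.1, and SAP 13 chose one side and disclosed the choice. Nor are events hidden. Excluded subjects are followed for 30 days and listed, SAP 8.1 counts intra-op exclusions in disposition, and Protocol 8.5 has deaths, drained effusions, atrio-esophageal fistulas and strokes reported to FDA.

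All of this stands. It makes the point one about a rule with no provision for a foreseeable case. It does not remove the point: disclosure and listing do not put an event into the primary rate.

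Three stronger readings are tempting but not supported:

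- *Exposed patients are being left out.* No passage says that access is begun before adhesions are found.
- *Only the convergent arm is affected.* The thrombus exclusion applies to both arms. ICE is itself invasive, so a control subject excluded on ICE may also be removed after an access step. Only the adhesion criterion is specific to the convergent arm.
- *One omitted event reverses the safety conclusion.* That holds only from 13/102 with the exact bound (20.4%). By Wald the same case gives 19.1% and passes; from 12/102 one added event passes by either method.

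**Conclusion.** The point holds as a gap in the definition of the safety analysis set. SAP 13 departs from Protocol 5.1 for all intra-op-excluded subjects on a premise that suits thrombus found on imaging but may not suit adhesions. Followed as written, it would keep an MAE from a started-then-aborted convergent procedure out of the primary rate.

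The size is small to moderate and its direction is not established. From the expected level (12/102), two omitted events among two or three such subjects take the exact bound just over 20%, to 20.2% or 20.1%, while the Wald bound stays below. One omitted event does not cross the limit by either method, and event-free subjects would lower the rate. These results rest on assumed values of k and e, on a starting count near the planned 12%, and on the inference that adhesions may be recognised after the incision. No figure stated in the plan is wrong on this point.

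**What to change.** In SAP 5.4 and 13, define the Safety Population as all subjects in whom the assigned procedure was started, whether or not it was completed. For the convergent arm, start means first incision. For the control arm, it means vascular access for the ablation procedure, with a statement of how exclusion on ICE is classed. Subjects excluded on imaging before any access stay in listings.

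For started-then-aborted subjects, open the MAE window and count the 30 days from that start date. Report the primary MAE rate with and without them, and name the interval method.

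A sentence in the SAP alone will not be enough. Protocol 5.1 (inclusion in the safety analysis), 8.0 (collection from coagulation) and 9.3.4 (receipt of a procedure), and SAP 3.2 (30 days from TEE or ICE), must be reconciled with the new definition.

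The cost is modest: short edits in both documents and recording of a start date for aborted cases. Follow-up for 30 days is already required, although its starting date would change for these subjects. The denominator shifts slightly, and the MAE rate may rise.
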